Therefore, the main objective of the study will be to compare the short- and medium-term effects of an EPMN intervention on the common peroneal nerve together with an exercise programme in relation to pain, ankle range of motion, ankle muscle strength, dynamic balance and function in both performance and self-report in patients with CAI. We hypothesised that those patients who receive neuromodulation combined with the neuromuscular exercise programme will have greater improvements in relation to the variables studied than those subjects who only receive the neuromuscular programme.

METHODOLOGY:

1. Participants:

Adult volunteers from the student body of the Escuela Universitaria Gimbernat Cantabria with a history of ankle sprain and physically active, defined as participation in moderate aerobic physical activity of at least 30 minutes 5 days a week, or vigorous intensity aerobic activity of at least 20 minutes 3 days a week (43), will be assessed to see if they can participate and be included in the study (44).

Inclusion Criteria: Subjects must meet the criteria:

1. History of at least one major ankle sprain. The initial sprain must have occurred at least 12 months prior to study participation, be associated with inflammatory symptoms (pain, oedema) and have resulted in at least one day of interrupted physical activity.
2. The most recent sprain must have occurred at least 3 months prior to study participation.
3. History in the injured ankle of "ankle wandering" (at least 2 episodes in the 6 months prior to study participation) and/or repeated sprains (two or more sprains in the same ankle) and/or feelings of instability in activities of daily living or sports (score less than 24 on the Cumberland Ankle Instability Tool (CAIT)).
4. Have a score of less than 75% in three or more categories on the FAOS (Foot and ankle Outcome Score) or a level of less than 90% in activities of daily living or a level of less than 80% in sports activities on the FAAM (Foot and ankle ability measure).
5. Pain on the VAS scale above 3 points out of 10 in physical activity.

Patients will be excluded from the study if they exhibit any of the following criteria:

1. History of surgery on either lower extremity that may interfere with the performance of the tests.
2. History of a fracture of either lower extremity requiring alignment.

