3. Acute injury to the musculoskeletal structures of other joints of the lower extremity within the previous 3 months, which impacts joint integrity and function resulting in at least one day of loss of physical activity.
4. Chronic concomitant pathology of the lower extremity (e.g. osteoarthritis, vascular disease, neural pathology).
5. Regular use of antalgic medication that may mask symptoms.
6. Contraindications to percutaneous puncture and to the performance of neuromodulation.
7. Receiving physiotherapy or medical treatment during the operation.
8. Being pregnant at the time of the start of the study.

2. Variables to be studied

2.1 Self-administered scales:

- **The Foot and ankle ability measure (FAAM)**, validated in Spanish (45), is a Likert scale consisting of 29 items, which have a score from 0 to 4, representing different levels of difficulty, divided into two subscales: activities of daily living (ADL) (21 items) and sports (8 items). The values are summed to calculate the score for each subscale, 84 points for ADLs and 32 points for sports (45). For the analysis of the score, the percentage of each subscale is used separately. The test-retest reliability is high, 0.89 for the ADLs and 0.87 for the sports subscale. In fact, the FAAM scale has been shown to be valid for use in patients with ankle instability. (46) It has been suggested that the minimum clinically important difference (MCID) is 8 and 9 points for the ADL subscale and for the sports subscale, respectively. (47)

- **The Cumberland Ankle Instability Tool (CAIT)**, validated in Spanish (48), has been shown to be a valid and reliable tool for assessing functional ankle instability (49). With an intraclass correlation coefficient (ICC) of 0.96, the CAIT scale has demonstrated excellent test-retest reliability. The scale consists of 9 items with a maximum score of 30 points, where higher scores indicate greater stability. It has been suggested that the MCID is 3 or more points (50).

2. 2 Measurements carried out by the therapist:

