In addition to the exercise programme, the experimental group will receive a session of EPMN on the common peroneal nerve of the affected lower limb. The EPMN will be applied prior to the exercise programme session. Three interventions will be performed, at a dosage of one per week. It will be performed with the electrostimulator (ES-160 ITO co.). (66) The participant will be placed in prone position with the foot outside the stretcher. The motor part of the common peroneal nerve affecting the innervation of the superficial peroneal nerve will be searched using an ultrasound machine (Chison Echo 5®, Chison Medical Technologies, China) with a high frequency (10 Hz) linear transducer. A dry needle (0.25mmx0.40mm, Agupunt®, Barcelona, Spain) will be introduced until it is close to the perineurium and a square wave biphasic electric current with a frequency of 2 Hz, a pulse width of 250 μ sec and a maximum tolerable intensity will be applied on the needle, with the aim of causing visible muscle contraction, according to the protocol of other studies. (37,42) Ten stimulations with a duration of 10 seconds will be performed, with a rest period of 10 seconds between each stimulation. The needle shall be kept still throughout the procedure and the skin shall be cleaned beforehand with isopropyl alcohol and chlorhexidine.

Assessment and follow-up:

The variables under study will be assessed at 3 different points in time: pre-intervention measurement, post-intervention (one week after the intervention), mid-term measurement (one month after the intervention).

Adverse effects:

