All patients will be asked to report any type of adverse event they may experience throughout the study and up to one month after completion. An adverse event is defined as a sequela of average duration with any symptom perceived as painful or unacceptable by the participant and requiring treatment (67). As needle insertion in some patients may induce post-treatment discomfort, subjects will be advised to report any incidences. EPMN has adverse effects that are infrequent and not serious, such as post-puncture pain that usually lasts from a few hours to a few days of mild intensity, the possible appearance of a haematoma that will be minimised thanks to the use of ultrasound and pressure techniques on the area, nerve irritation that will be minimised as much as possible by the use of ultrasound again and finally the possibility of infection, so a disinfectant will be used on the area before the technique and single-use gloves. The therapeutic exercise programme has subsequently been used by other research groups and is very safe because it is an incremental programme adapted in intensity individually to each

subject. Possible adverse effects are also rare, where the most common may be increased ankle pain, which will be controlled by adapting the load, the possible generation of delayed onset muscle soreness, which usually has a peak duration of 48 hours and a possible fall with instability and disturbance work, which is minimised by the presence of the therapist monitoring the session at all times.

Sample size calculation:

The sample size and power calculation was calculated with the software G-Power 3.1.9.4 (Heinrich Heine Universität Düsseldorf) (68). Calculations were based on the detection of an 8-point mean difference (MCID) on each FAAM scale (46), assuming a standard deviation of 6.5, a 2-tailed test, an Alpha level of 0.05 and a desired power of 90%. The estimated sample size is 15 participants per group.

Statistical analysis of data:

1. Descriptive data in mean, range and standard deviation.
2. Normal distribution/homoskedasticity of the data (See whether the data are parametric or non-parametric). Kolmogorov-Smirnov test and Levene's test.
3. Comparison of means between two groups (experimental group and placebo control group) using Student's t-test to analyse the differences between the quantitative dependent variables of the study. If the data are non-parametric, we will use the Wilcoxon statistic.

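### No primary outcome, visit, success rule or multiplicity control is stated, so the single 0.05 and 90% are right for one FAAM test but do not both describe a conclusion drawn from the four FAAM tests.

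*Combined protocol and SAP*

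**What the plan says.** The Introduction sets no order among outcomes or time points. It says "the main objective of the study will be to compare the short- and medium-term effects" on pain, range of motion, strength, balance and function. The hypothesis is that patients given the combined treatment "will have greater improvements in relation to the variables studied than those subjects who only receive the neuromuscular programme".

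The Sample size calculation is the only place where an outcome is singled out: "Calculations were based on the detection of an 8-point mean difference (MCID) on each FAAM scale (46". It uses an SD of 6.5, a two-tailed alpha of 0.05 and 90% power, and arrives at 15 per group. It names no visit.

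On FAAM, section 2.1 says: "For the analysis of the score, the percentage of each subscale is used separately". The two subscales are activities of daily living (ADL) and sports. Assessment and follow-up lists, after baseline, "post-intervention (one week after the intervention), mid-term measurement (one month after the intervention".

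Statistical analysis of data, item 3, compares the groups "using Student's t-test to analyse the differences between the quantitative dependent variables of the study", and adds: "If the data are non-parametric, we will use the Wilcoxon statistic". Item 4 computes Cohen's d for the pre-to-post difference. No section names a primary outcome, a primary visit, a rule for success across several tests, an order of testing or a multiplicity adjustment.

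**The concern.** An alpha of 0.05 and a power of 90% are properties of one decision, and the plan does not say which decision. Even if FAAM is taken as the intended basis, two subscales at two follow-ups give four tests, and item 3 tests every other quantitative variable as well.

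As written, a positive conclusion could rest on whichever test reaches significance, or could be withheld unless all do. Under the first rule, an ineffective add-on has more than the nominal chance of appearing beneficial. Under the second, the trial has less than its stated power. A choice made after the between-group results are seen cannot repair this credibly.

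Even the single comparison is not fully defined. Item 3 does not say whether follow-up values or changes from baseline are compared, and the choice of test depends on the data. These gaps are separate from multiplicity and do not enter the figures below, but the same paragraph of the plan should close them.

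**Working it through.** **Inputs from the documents**
- Difference 8, SD 6.5, two-tailed 0.05, target power 90%, 15 per group (Sample size calculation).
- Two subscales, with minimum important differences of 8 (ADL) and 9 (sports) (section 2.1).
- Two follow-ups (Assessment and follow-up).

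**Assumed inputs.** The documents give no correlations between the trial's tests, so a range is used.
- Between subscales: 0 to 0.8.
- Across visits: 0.5 to 0.88. The upper end follows section 2.1: "The test-retest reliability is high, 0.89 for the ADLs and 0.87 for the sports subscale". The mean, (0.89 + 0.87)/2 = 0.88, is a rough ceiling for raw scores. The lower end applies to change scores. If raw scores have equal variance s² and equal correlation r over the three visits, two changes sharing a baseline have covariance s²(1 − r) and variance 2s²(1 − r), so their correlation is 0.5 whatever r is.

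**Step 1: reproduce the plan's figure.** d = 8/6.5 = 1.231. With n = 15 per group, the noncentrality is 1.231 × √(15/2) = 3.371, there are 28 degrees of freedom and the critical t is 2.048. Power from the noncentral t is 0.902, against 0.880 at 14 and 0.853 at 13. So 15 per group is right for one test.

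**Step 2: count the tests.** 2 subscales × 2 follow-ups = 4.

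**Step 3: simulate four t-tests at 15 per group.** The correlation matrix is subscale × visit (Kronecker product), with 300,000 to 600,000 replicates per case. Each range runs from subscale correlation 0 to 0.8.

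| Correlation across visits | Any of four, no effect: two-sided error | Any of four, no effect: false benefit | All four, true effect 8 and 8: power | All four, true effect 8 and 9 (sports): power |
|---|---|---|---|---|
| 0.5 | 0.174–0.142 | 0.089–0.071 | 0.697–0.766 | 0.767–0.813 |
| 0.8 | 0.151–0.122 | 0.077–0.061 | 0.736–0.800 | 0.799–0.840 |
| 0.88 | 0.141–0.113 | 0.071–0.057 | 0.751–0.811 | 0.813–0.850 |

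The nominal false-benefit rate is 0.025, so the ratio runs from 0.057/0.025 = 2.3 to 0.089/0.025 = 3.6.

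**Step 4: two subscales at one visit.**
- Both required, 8 points on each: 0.902² = 0.814 at zero correlation, 0.858 at 0.8.
- Both required, 9 points for sports: single-test sports power is 0.955, so 0.902 × 0.955 = 0.861 at zero correlation, 0.889 at 0.8.
- Either may count, no effect: two-sided error 0.098 to 0.079, false benefit 0.049 to 0.039.

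**Step 5: what does not fail.** Under an any-result rule, power is at least that of one test, so 90% is met. Under an all-results rule, error cannot exceed 0.05. One property fails under each rule.

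**The case against.** The strongest reply is that FAAM is the implied primary outcome because it drives the sample size, and that item 4's pre-to-post wording points to the post-intervention visit. The improvement wording of the hypothesis, together with item 4, also leans towards change scores. These are fair hints, but they settle neither the visit nor the quantity. The main objective covers the short and the medium term alike, and accepting every hint still leaves two subscales and no rule for combining them.

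A second reply is that no section says a single significant result will be claimed as success. That stands. The inflated error is conditional on a rule the plan does not state, and so is the power loss. It also stands that the power loss is milder if 9 points is the sports difference, as section 2.1 suggests.

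A reader might infer more than the documents support:
- *That the sample size is wrong.* It reproduces exactly for one test.
- *That both alpha and power fail.* Only one does under each rule.
- *That the error is 18.5% (1 − 0.95⁴), with false benefit 9.6% (1 − 0.975⁴).* That needs four independent tests, which is implausible for one questionnaire measured on the same people.
- *That testing every other variable adds a known amount.* More tests can only raise an any-result error, but the amount would rest on further assumed correlations.
- *That one time horizon must be demoted or more participants recruited.* A fixed sequence avoids both.

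**Conclusion.** The concern holds in this form: the decision is undefined, and the stated 0.05 and 90% do not together describe a conclusion drawn from the four FAAM tests.

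- **If any of the four may count:** two-sided error about 11 to 17%; false benefit about 5.7 to 8.9% instead of 2.5%.
- **If all four must succeed:** power about 70 to 81% with 8 points on each subscale, or about 77 to 85% with 9 for sports.
- **If both subscales at one visit must succeed:** power 81 to 86%, or 86 to 89% with 9 for sports.

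These figures assume the stated correlation ranges, t-tests, an SD of 6.5 for every quantity tested and all 15 per group evaluable. The direction does not depend on the correlation chosen within the ranges. This should be fixed before any between-group result is seen.

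**What to change.** Before any between-group result is seen, amend the sample-size and analysis sections as follows.

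1. Name one FAAM subscale at one follow-up as the primary comparison at two-sided 0.05.
2. State whether it compares follow-up values or changes from baseline, that the SD of 6.5 refers to that quantity, and the one test to be used whatever the normality check shows.
3. Test the other subscale and the other follow-up in a prespecified fixed sequence, each at 0.05 and only if the previous test is significant. This holds overall error at 0.05 and keeps both the short- and medium-term objectives.
4. Label all remaining variables secondary, reported as between-group differences with 95% confidence intervals.
5. State that 90% power applies to the first comparison only, with 15 evaluable per group (88.0% at 14, 85.3% at 13).

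**Cost.** This is a change of wording with no added participants under the plan's own assumptions. The price is that a later test cannot be claimed if an earlier one fails, and that power falls along the sequence. With 8 points throughout, it is 81 to 86% for reaching significance on both subscales at one visit and about 70 to 81% for completing all four tests.

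If the sponsor wants tests that can be claimed independently, Bonferroni over two or four gives per-test power of 83.5% or 75.3% at 15 per group. Restoring 90% per test would need 18 or 21 evaluable per group, that is 3 or 6 more.

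### Fifteen per group leaves no room for loss, and the planned two-group t-test discards the one-week score of anyone missing at one month; one mixed model would keep it

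*Combined protocol and SAP*

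**What the plan says.** Under 'Sample size calculation' the plan states "Calculations were based on the detection of an 8-point mean difference (MCID) on each FAAM scale", "assuming a standard deviation of 6.5", with "a 2-tailed test, an Alpha level of 0.05" and 90% power, computed in G-Power. It concludes "The estimated sample size is 15 participants per group". No expected loss and no inflation follow.

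Under 'Assessment and follow-up', "The variables under study will be assessed at 3 different points in time": before the intervention, one week after it and one month after it.

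Under 'Statistical analysis of data', item 3 compares the two groups "using Student's t-test to analyse the differences between the quantitative dependent variables of the study", with a Wilcoxon fallback. Item 4 adds a Cohen's d for pre to post. Neither the analysis section nor any other names an analysis set, a rule for missing visits, a model covering both follow-ups, or the visit to which the t-test applies.

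Under 'Randomisation', participants are stated to know their allocation.

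**The concern.** There are two linked gaps. First, the size is given as a number of participants, but the calculation behind it needs that many measured outcomes. Any missed visit takes power below the stated figure.

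Second, a two-group t-test uses one score per person. Applied to the one-month score, it cannot include a participant who did not attend then, even if the same outcome was recorded three weeks or so earlier. Three weeks of treatment plus one month makes about seven weeks in the study, and controls know that they did not receive the needle technique. Loss that depends on how a participant is doing, and that differs between arms, is therefore possible. Under such loss the groups compared at one month are no longer the groups that were randomised, and the planned test has no means of correcting for it.

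**Working it through.** **Reproducing 15 per group.** Inputs, all from the sample size section: difference 8, SD 6.5, two-sided alpha 0.05, power 90%. The method is the two-sample t-test with the noncentral t distribution, as G-Power does it.

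- d = 8/6.5 = 1.231
- df = n1 + n2 − 2
- noncentrality = 8 / (6.5 × √(1/n1 + 1/n2))

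For 15 and 15: df = 28, critical t = 2.048, noncentrality = 3.371, power = 0.902. Solving for exactly 90% gives 14.90 per arm, so 15 is only that figure rounded up.

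**Power after loss, same formula:**

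| Measured per arm | Power |
|---|---|
| 15 / 15 | 0.902 |
| 15 / 14 | 0.891 |
| 14 / 14 | 0.880 |
| 13 / 13 | 0.853 |
| 12 / 12 | 0.8215 |

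The documents give no loss rate. Over an assumed range, random loss of 5%, 10%, 15% or 20% from 15 per group gives average power of 88.4%, 86.4%, 84.1% and 81.4%. The chance of losing at least one of 30 is 1 − 0.95^30 = 79% at 5% loss and 1 − 0.90^30 = 96% at 10% loss.

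**Bias at one month.** This part rests on assumptions, none of them from the documents except the SD and the 8 points:

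- the correlation between the one-week and one-month scores is 0.7 (range 0.5 to 0.8);
- 60% of the worst third of controls at one week miss the one-month visit, which is 0.6 × 5 = 3 of 15;
- nobody is lost in the other arm.

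For a normal score the worst third lies below z = −0.431, where the normal density is 0.364. The remaining 80% of controls have a one-week mean raised by 0.6 × 0.364 / 0.8 = 0.273 SD. Their one-month mean is raised by 0.273 × 0.7 × 6.5 = 1.24 points. The expected per-visit estimate is therefore 8 − 1.24 = 6.76.

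Simulation with 20,000 trials per scenario agrees:

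| Loss pattern | Correlation | Per-visit t-test difference | Using the one-week scores |
|---|---|---|---|
| Worst controls only | 0.5 | 7.1 | 8.0 |
| Worst controls only | 0.7 | 6.8 | 8.0 |
| Worst controls only | 0.8 | 6.6 | 8.0 |
| Worst third, both arms equally | 0.7 | 8.0 | 8.0 |
| Best controls only (opposite pattern) | 0.7 | 9.2 | 8.0 |

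With equal loss in both arms the only gain from the one-week scores is precision: the standard error falls from about 2.67 to 2.53. In the first pattern at correlation 0.7 the per-visit test has about 75% power, against 86.3% for random loss of the same three controls (15 / 12).

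**The case against.** The figures are not in dispute, but several limits on them are fair.

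- **The power loss starts small.** A reader might infer that the 90% claim collapses with the first drop-out. That drop-out costs 1.1 percentage points (90.2% to 89.1%), and three losses per arm still leave 82%. Rounding up to 15 is ordinary practice. What is missing is a statement of what happens with loss.
- **Complete-case testing at each visit is not written in the plan.** A reader might take it as prescribed. Item 3 does not say which visit, whether raw or change scores, or which participants. What stands is narrower: a two-group test of a one-month score cannot use a person who has none.
- **A reader might infer that the one-month comparison is biased.** The documents do not support that. They give no loss rate, no reasons for loss and no correlation between visits. Supervised sessions, a three-week programme and volunteers from one school suggest modest loss, although no figure is given. Bias needs loss that is both related to scores and different between arms. If only about one such control is lost, the estimate is about 7.7. Even the full scenario shifts it by 1.2 points against a standard error of about 2.5, and towards the null.
- **The recovery to 8.0 follows from the set-up.** The simulated loss depends only on the observed one-week score, which is exactly what a likelihood analysis assumes. Loss driven by unrecorded scores would not be fully corrected.
- **A model holding only the two follow-ups would still omit anyone lost before one week.** This stands, and the change below meets it by including baseline.
- **The sports subscale has slack on its own MCID.** With the 9 points quoted under 'Variables to be studied', power is 95.5% at 15 / 15 and 90.0% at 12 / 12. But the stated calculation uses 8 points for each scale.

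**Conclusion.** The concern holds in a limited form. From the plan's own inputs, 15 per group carries no allowance for loss, and the 90% figure requires all 30 participants to be measured at the visit analysed. Power is 88%, 85% and 82% with one, two or three lost per arm. This part rests on no outside assumption.

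The bias is conditional. It arises only if loss is linked to earlier scores and differs by arm, which the open allocation makes possible but which nothing in the documents shows. Under the assumed loss of about 3 of 15 controls, a true 8 points is estimated as 6.6 to 7.1 across correlations 0.8 to 0.5. Its direction depends on who leaves. The case for change is that a better analysis is available on data already being collected, in software already planned; it does not rest on any demonstration that the planned result would be wrong.

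**What to change.** 1. Replace the t-tests with one mixed model per outcome: arm, visit and arm × visit, with unstructured covariance. Enter both follow-ups and the baseline score as visits, so that participants lost before one week are also retained. Include all randomised participants in their assigned arm, and read the one-week and one-month contrasts from the model.
2. Restate the power sentence: 90% if all 30 are measured; 88%, 85% and 82% if one, two or three per arm are lost.

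Cost: wording in the analysis section and one SPSS MIXED procedure per outcome, with no extra participants or visits. The stated power becomes slightly less favourable. The model assumes that loss depends on observed scores. With complete data the gain from holding the second follow-up is negligible.

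If the sponsor would rather keep 90% after loss, the alternative is to state an expected rate d and recruit 15/(1 − d) per group: 17 at 10% (15/0.90 = 16.7) or 19 at 20% (15/0.80 = 18.75). Both rates are assumptions, and this option does cost participants.

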After baseline assessment patients will be randomly assigned to receive a neuromuscular exercise programme (control group) or to receive a neuromuscular exercise programme plus a common peroneal nerve EPMN (experimental group). Concealed allocation will be performed using a computer-generated random table of numbers created prior to data collection by an external investigator. Individualised, sequentially numbered index cards will be prepared. These will be placed in sealed opaque envelopes and the second external researcher will open the envelope and proceed with the treatment according to the allocation.

Each group will be treated by a physiotherapist clinician, who will be the principal investigator of the study, with more than 15 years of experience in the management of lower limb

musculoskeletal injuries and more than 10 years of experience in the management of invasive techniques and ultrasound assessment.

The researcher conducting the data processing will be blinded to group membership and the researchers conducting the assessments will be blinded to the participant's group assignment. Participants in this study will not be blinded to their group assignment. All participants will read and sign an informed consent form prior to inclusion in the study and will be asked to lead a lifestyle identical to the one they were leading prior to the start of the study.

4. Procedures:

Neuromuscular exercise programme:

The combination of strength exercise and dynamic balance exercise has been shown to be more effective than strength work alone in the management of CAI (63). The exercise programme applied in the intervention is based on the best available evidence and is common practice in the clinic. All exercises will be performed under the supervision of the therapist. A 3-week intervention will be performed with two sessions per week.

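### Normality and variance pre-tests choose between Student's t and Wilcoxon for each outcome and visit, so the inferential target depends on the data; type I error drifts materially only if SDs and arm sizes both differ

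*Combined protocol and SAP*

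**What the plan says.** In the combined protocol and SAP, item 2 of 'Statistical analysis of data' examines normality and homoskedasticity in order to label the data parametric or non-parametric, using the "Kolmogorov-Smirnov test and Levene's test". Item 3 compares the two groups "using Student's t-test to analyse the differences between the quantitative dependent variables of the study", and adds: "If the data are non-parametric, we will use the Wilcoxon statistic".

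The section does not give a significance level for the pre-tests, or say whether they apply per arm or pooled, to raw scores or to changes. It does not say what a Levene failure alone triggers, or whether Wilcoxon means the rank-sum or the signed-rank test. It mentions no unequal-variance t-test and no confidence interval. Item 1 reports means, ranges and standard deviations; item 4 adds a pre-post Cohen's d.

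The 'Sample size calculation' works on means: "Calculations were based on the detection of an 8-point mean difference (MCID) on each FAAM scale", "assuming a standard deviation of 6.5", with "a 2-tailed test, an Alpha level of 0.05 and a desired power of 90" per cent. It concludes: "The estimated sample size is 15 participants per group". Section 3, 'Randomisation', states: "Concealed allocation will be performed using a computer-generated random table of numbers". No blocking is described, and no dropout allowance is given.

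**The concern.** The trial is sized to detect a difference in mean FAAM score. If FAAM fails a pre-test, the inference concerns rank ordering instead, and the result cannot be set against the 8-point MCID with an interval around it. Because the choice can be made afresh for each variable and follow-up, one outcome could be tested on means at one week and on ranks at one month.

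The pre-tests are also weak gatekeepers at this size. They divert some well-behaved data by chance and let many real departures through. Outcomes that pass go to the equal-variance t-test, whose standard error is wrong when SDs and arm sizes both differ. Outcomes that fail go to a rank test, which does not correct for unequal variances either.

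**Working it through.** **1. The plan's own figure.** The standardised difference is 8/6.5 = 1.231. The normal approximation gives 2 × (1.960 + 1.282)² / 1.231² = 13.9, so 14 per group. The exact noncentral-t calculation gives power 0.880 at 14 and 0.902 at 15. The stated 15 per group is reproduced.

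**2. How often sound data switch.** Take normal data with equal SDs at 15/15 and pre-tests at 0.05 (assumed). With the Lilliefors correction in each arm, the chance that at least one arm fails is 1 − 0.95² = 0.0975. Levene rejected in 5.4% of simulated trials. Together: 1 − 0.9025 × 0.946 = 0.146, about 15%. With uncorrected Kolmogorov-Smirnov plus Levene, simulation gives 5.7%, nearly all of it from Levene. Counting 14 outcomes (FAAM 2, CAIT 1, side hop 1, CMJ 1, strength 3, SEBT 3 plus composite, NPRS 1, ROM 1) at two follow-ups gives 28 comparisons. Expected switches are 28 × 0.057 = 1.6 to 28 × 0.15 = 4.2.

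**3. What the pre-tests miss.** Levene fails to detect an SD ratio of 1.5 in about 73% of trials and a ratio of 2 in about 39%.

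**4. Why arm balance matters for Student's t.** Take SDs of 2 and 1.
- 15/15: the true variance of the difference is 4/15 + 1/15 = 0.333. The pooled version is 2.5 × (2/15) = 0.333. They agree.
- 10/20, larger SD in the smaller arm: true 4/10 + 1/20 = 0.450. Pooled variance is (9×4 + 19×1)/28 = 1.964, times (1/10 + 1/20) gives 0.295. The standard error is too small.
- 10/20, larger SD in the larger arm: true 1/10 + 4/20 = 0.300. Pooled variance is (9×1 + 19×4)/28 = 3.036, times 0.15 gives 0.455. The standard error is too large.

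**5. Type I error of the two-stage rule.** Simulation with 40,000 trials per setting, equal means, normal data, Lilliefors per arm and mean-based Levene, each at 0.05. SD ratios and splits are assumptions, because the documents give none. Ranges cover SD ratios 1.5-2 and repeated runs unless marked.

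| Split, arm with larger SD | Levene failure to Wilcoxon | Levene failure to Welch |
|---|---|---|
| 15/15 | 4.8-5.5% | about 5% |
| 13/17, smaller arm | 5.9-6.8% | 6.1% (ratio 2) |
| 10/20, smaller arm | 7.5-9.3% | 7.2-7.7% |
| 17/13, larger arm | about 4% (ratio 2) | up to about 5% (ratio 2) |
| 20/10, larger arm | 2.4-3.1% | 3.8% |

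If Levene had no consequence at all, the figures at ratio 2 with the larger SD in the smaller arm are 8.7% at 12/18 and 11.4% at 10/20. With equal SDs, the rule with Levene failures sent to Wilcoxon stays at 5.0-5.3% at 15/15, 12/18 and 10/20. At 15/15 with an SD ratio of 3 it reaches 6.6%.

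**6. Chance of unequal arms.** If 30 people were allocated without restriction (an assumption), exactly 15/15 has probability C(30,15)/2³⁰ = 0.14, 13/17 or worse 0.58, and 10/20 or worse 0.10.

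**7. Welch without pre-tests.** On normal data its type I error is 4.7-5.2% across these settings. With an assumed left-skewed shape it is 4.6-7.2%. Power for 8 points at SD 6.5, Student against Welch, is 90.3% and 90.2% at 15/15, 88.8% and 88.3% at 12/18, and 86.8% and 85.1% at 10/20.

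**The case against.** The strongest reply is that the planned trial has 15 per arm and one assumed SD, and under those conditions the rule keeps its error rate. That stands. A reader might infer that pre-testing by itself inflates type I error; the calculations do not support this, and the documents give no unequal SDs, no realised imbalance and no dropout rate. Chance imbalance also favours neither direction. Averaged over both directions at SD ratio 2, the error is about 5.3% at 13/17 and 5.6-5.8% at 10/20. It remains wrong conditional on the arms actually obtained, and dropout could be directional.

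Second, a reader might take it as stated that a Levene failure leads to Wilcoxon. Item 2's wording implies this but does not say it. The name of the analysis package, SPSS, is in 'Data management', and SPSS prints an unequal-variance row beside Student's t, so Levene could be meant to select that row. The drift is then smaller at 10/20 but does not vanish.

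Third, a reader might infer that a Wilcoxon outcome leaves no mean difference at all. Item 1 still reports group means and SDs, so the difference can be calculated. What is missing is a confidence interval belonging to the test.

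Fourth, Welch is not exact for every shape. FAAM, CAIT and NPRS are bounded scores, so normality is the favourable case. Skewness does not rescue the planned rule, however. With the assumed left-skewed shape, SD ratio 2 and equal arms of 15, Wilcoxon read as a test of equal means rejects in 10.3% of trials and the two-stage rule in 9.3%, against 5.8% for Welch.

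**Conclusion.** The point holds on prespecification. The choice of test, and with it the inferential target, depends on the data for each outcome and visit, and the rank branch carries no interval for the FAAM mean difference. Some 6% to 15% of comparisons with ideal data would switch by chance.

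The error-rate part is conditional. With normal data it is about 5-6% at 15/15 for SD ratios up to 2, and near 5% whenever SDs are equal. With the larger SD in the smaller arm it rises to about 6-7% at 13/17 and 7.5-9% at 10/20 (slightly lower at 10/20 if Levene leads to Welch). With the larger SD in the larger arm it is about 4-5% at 17/13 (SD ratio 2) and 2.5-4% at 20/10. These figures rest on assumed SD ratios of 1.5-2, assumed splits that unblocked allocation or dropout could produce, and pre-tests at 0.05. The sample size of 15 per group is correct for its inputs and is not affected. The rule should be changed, but the documents do not support saying that the trial as planned has an inflated type I error.

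**What to change.** Delete the pre-tests as a decision rule; distributions can still be described. Prespecify one analysis for every quantitative outcome at each follow-up: either Welch's t-test, or a linear model adjusted for the baseline value with heteroscedasticity-robust standard errors. Report the between-group mean difference with its 95% confidence interval, so that FAAM can be read against the MCID. Keep the rank test as a sensitivity analysis only, named as the Wilcoxon rank-sum (Mann-Whitney) test.

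This takes about two sentences in items 2-3 and, for Welch, no new software. For Welch against Student's t, the power cost at the sizing assumptions is about 0.1 percentage point at 15/15, 0.5 at 12/18 (88.8 − 88.3) and 1.7 at 10/20 (86.8 − 85.1).
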